#### **Patient follow-up**

All women who participate in this trial will be asked to return at 4 weeks post-discharge. At this time, general puperum care will be arranged for the study participants and their babies. All adverse events or complications will be documented and treated accordingly. The participants' acceptability and satisfaction level considering their involvement in the trial will also be evaluated.

# SAFETY MONITIORING AND QUALITY ASSUARANCE Interim analysis

We will perform an interim analysis after the first 30 participants in each arm have been

enrolled. This analysis will be examined by the Data and Safety Monitoring Committee comprising of: [name] (Director of Health Research, Divine Word University), [name] (independent onsite Obstetrician, Modilon Hospital), [name] (UPNG, Paediatrician), [name] (PNGIMR, Head of Vector Borne Unit), and [name] (WEHI, Melbourne – scientist and statistician).

This committee will review the results of the interim analysis and decide on the progress of the study. The three criteria to be used will include **i**) drug related adverse events >25% documented within 72 hours post-administration of treatment, **ii**) severe adverse events >10% documented within 72 hours post-administration of treatment, and/or **iii**) >25% adverse events reported at 4 weeks post-discharge.

The second interim analysis will be performed after 80 patients in each arm of the trial have been enrolled. All study protocols will be adhered to at all times and any deviation to the study protocols will not be administered without appropriate ethical approval.

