#### **ETHICAL ISSUES**

We have experience in conducting research in this setting [10-12] and do not anticipate that we will be encountering serious ethical issues during the conduct of this study. However, some ethical issues that we may confront include:

- Age of consent: Because teenage pregnancy is common in our setting, we will ensure only women over the age of 18 are eligible for inclusion in this study.
- Written Informed Consent Procedures: Women who fulfil the selection criteria for induction of labour and are eligible and willing to participate in the trial will be asked to complete formal written informed consent procedures that will include face-to-face discussion with the investigator or designated staff member of the clinical trial team who will then explain key study objectives, procedures, potential risks and benefits in more

detail. This will include a clear explanation that participation in this trial is entirely voluntary, and that withdrawal is possible at any time without having to give a reason.

- **Patients' autonomy**: We are aware of the challenges involved when clinical research is integrated with patient care in resource-limited settings such as ours [13]. However, the study protocol will be adhered to at all times and no deviation to the study protocol will be entertained without proper ethical approval.
- **Patient confidentiality**: Each study participant will be assigned a study code and we will separate the patients name from the information and samples collected. We will be very careful about the information that we collect, ensuring this information is made available only to the doctors or nurses providing patient-care.

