## **CANDIDATURE TIMELINE**

The time as proposed by the University of Papua New Guinea By Law No:37 governing the Degree of Doctor of Medicine-Part 2 states that candidates admitting to the degree by presentation of a thesis would be required to complete 3-5 years. Therefore, I would like to complete my MD within 3 years.

During the 3 years of this MD program (2016-2018), I will spend most of the time continuing in my capacity to do clinical work and conduct these studies as part of continued professional education and research. I will spend some time to supervise, coordinate and train the staff about the study protocol and methods on a daily basis.

I hope to complete the proposed study by 2017 and to perform data analysis and write up in 2018. My detailed candidature timeline is proposed below:

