## 2016

- January Submit Draft Research Proposal
- **February** Literature Review
- February Submit corrected draft Research Proposal to supervisors
- March Enrol for MD Program and submit Final Research Proposal
- March-April Submit for Ethical Approval from MHEC, MRAC, UPNG SMHS Ethics
  committee and register the trial
- April Commence data collection
- June Start Preliminary data entry and continue literature review
- August Continue research and data entry
- September Perform interim analysis on the first 30 participants (each arm)
- October Continue literature research and start writing background of thesis
- November Start writing methodology of the thesis
- **December** -Start writing 2016 annual report

- February Submit 2016 annual report to UPNG, SMHS post graduate office
- March Continue writing thesis background and methodology
- May Aim to have recruit 80 participants in each arm and to perform the second interim analysis
- June Continue writing methodology of thesis and data entry
- November Required number for the study (236 in total) to be completed

• **December** Start writing 2017 Annual Report

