# **ETHICAL APPROVAL**

The study will obtain ethical clearance from Modilon General Hospital Ethics Committee (MHEC), UPNG SMHS Ethics committee, Medical Research Advisory committee of Papua New Guinea (MRAC) and the trial will be registered with International Standard Randomized Control Trial(ISRCTN) Registry and attain a RCT number. It will be conducted under Good Clinical Practice guidelines and monitoring and safety evaluation will be performed by an independent Data and Safety Monitoring Committee.

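### The interim analyses are assigned to the treating investigators with no stated limit on access to the results, although independent monitoring is promised

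*Protocol*

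**What the plan says.** The Protocol's interim analysis section gives the first look to the trial team: "We will perform an interim analysis after the first 30 participants in each arm" are enrolled. The Data and Safety Monitoring Committee then examines that analysis and decides whether the study goes on. The committee's listed members include a scientist who is also a statistician.

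For the second look the same section names no performer: "The second interim analysis will be performed after 80 patients in each arm of the trial have been enrolled". The Candidature Timeline fills the gap. It is the candidate's own work plan, and it contains both "Perform interim analysis on the first 30 participants (each arm") and, for the following year, "Aim to have recruit 80 participants in each arm and to perform the second interim analysis".

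The same part of the Protocol describes the candidate's role during the trial: "I will spend most of the time continuing in my capacity to do clinical work and conduct these studies". Under Study design, the trial is open-label, and study medical or nursing staff open the allocation envelopes.

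The Ethical Approval section states that "monitoring and safety evaluation will be performed by an independent Data and Safety Monitoring Committee".

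**The concern.** The committee is meant to be independent, but what it examines is compiled by the people it monitors, and nothing keeps the compiled results from those who recruit and treat. An open label already shows staff single cases. Assembled event rates are different, because they can create a belief about how one regimen compares with the other.

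Such a belief can act on decisions still to be made: whom to approach, when an induction is judged to have failed and goes to caesarean, and which babies go to the special care nursery. The last two are components of the primary endpoint. The Sample Size Calculation tests non-inferiority against a difference of 5 percentage points, so modest shifts in such decisions could matter.

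This is more than detail that a SAP would supply, because the Protocol itself names who does the analysis.

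**Working it through.** **Who does what, side by side**

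| Question | Where in the Protocol | Answer |
|---|---|---|
| Who performs look 1? | Interim analysis; Candidature Timeline | The investigators; also a task of the candidate |
| Who performs look 2? | Interim analysis; Candidature Timeline | Not named in the first; a task of the candidate in the second |
| Who examines the results and decides? | Interim analysis | The committee |
| Who evaluates safety? | Ethical Approval | An independent committee |
| Does the candidate treat patients? | Candidature Timeline | Yes, clinical work continues |
| Is treatment masked? | Study design | No, open-label |
| Is access to interim results limited? | Nowhere | Not stated |
| Are results by arm or pooled? | Interim analysis | Not stated |

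**Is tabulation by arm likely?** The three stopping criteria (over 25%, over 10%, over 25%) are absolute event rates and are not labelled per arm or pooled. Two features point to tables by arm: each look is triggered by a count in each arm, and the Specific aims and Data Analysis Plan frame safety and efficacy as comparisons between arms. This is an inference, not a statement of the Protocol.

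**The total of 236.** This is the denominator for what follows. The Protocol gives no control success rate. With an assumed 90% on standard treatment and 95% on low dose, margin 5 points, one-sided 5% and 90% power:

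n per arm = (1.645 + 1.282)² × (0.90 × 0.10 + 0.95 × 0.05) / (0.05 + 0.05)² = 117.8, rounded up to 118, total 236.

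This matches the stated figure. Assumed control rates of 85% and 91% would give 374 and 208.

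**Recruitment left after each look**

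- Look 1: 2 × 30 = 60 women, leaving 236 − 60 = 176, and 176/236 = 74.6%.
- Look 2: 2 × 80 = 160 women, leaving 236 − 160 = 76, and 76/236 = 32.2%.

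**Allowing for delay.** The third criterion needs events reported 4 weeks after discharge. The timeline goes from 60 women in September 2016 to 160 in May 2017, so 100/8 = 12.5 a month. If recruitment continues and results come 1 to 2 months after the trigger (an assumption), look 1 leaves:

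- 1 month: (176 − 12.5)/236 = 69.3%
- 2 months: (176 − 25)/236 = 64.0%

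**Direction of any bias.** Take, as an assumption, true success of 90% on standard and 85% on low dose, so that low dose is worse by exactly the margin. Exact binomial calculation gives:

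| Look | Low dose ahead | Level | Low dose behind |
|---|---|---|---|
| 30 per arm | 21% | 13% | 65% |
| 80 per arm | 14% | 6% | 80% |

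Staff who saw these results would more often form a view against low dose than for it. At 30 per arm, the 95% half-width for the difference is 1.96 × √(0.90 × 0.10/30 + 0.85 × 0.15/30) = 0.167, about 17 points, so look 1 says little about a 5-point difference. Neither the direction nor the size of a bias can be derived from the Protocol.

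**The case against.** **Preparing a report is not evaluating it.** The committee examines the analysis and decides, so the promise of independent evaluation is not flatly broken. This stands. A reader might infer a direct contradiction between the interim analysis and Ethical Approval sections, but the text does not support that. What remains is that the committee's input is made by the investigators, with no stated limit on who sees it.

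**Tables by arm and the team's knowledge are inferred.** This also stands. A reader might conclude that the team will know the arm-level results for three-quarters of recruitment. The Protocol supports only that it could, if tables are by arm, and three-quarters is an upper bound.

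**The bias need not favour low dose.** A reader might expect interim knowledge to raise the chance of wrongly declaring non-inferiority. That needs a shift towards low dose. When low dose is truly worse, the looks would usually show it behind. No inflation of the false-positive rate should be claimed.

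**The confidentiality sentence.** The Ethical Issues section says of collected information, "ensuring this information is made available only to the doctors or nurses providing patient-care". A reader might take this to shut the committee out. It stands under patient confidentiality, next to study codes and the separation of names, and the interim section expressly gives the committee the results. It is not evidence here.

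**The open label limits the gain.** Staff open the envelopes and the candidate's plan includes data entry, so the team could build its own tally. This stands in part: the protection is incomplete. But not routinely compiling rates for the treating team still removes one avoidable source of influence.

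**This belongs in a committee charter.** Access rules often do. Here, however, the Protocol already assigns the task, and assigns it to the trial team, so a charter would have to override it.

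**Conclusion.** The point holds in a limited form. The Protocol assigns the first interim analysis to the investigators, and the candidate's timeline assigns both. The candidate also treats patients in this open-label trial, and no limit on access to the results is stated. This sits poorly with the promised independent monitoring without contradicting it outright.

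The size that can be stated is exposure, not bias: up to 75% of women still to be enrolled after look 1 (about 64-69% with a delay of 1 to 2 months) and up to 32% after look 2. Those figures rest on the planned 236 women, on the timeline's pace and, for any comparative knowledge, on tables being by arm. The effect on the conclusion is of unknown size and direction. It is a cheap improvement worth making, not a flaw that invalidates the design.

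**What to change.** Reword the interim analysis section and the two timeline entries so that:

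- the statistician already on the committee receives coded data with the allocation list and prepares any arm-level interim tables for the committee only;
- the investigators supply the data, see pooled totals over both arms, and receive only the committee's recommendation.

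The cost is protocol wording and some of the committee statistician's time, with no extra patients. The investigators give up sight of aggregate arm-level results until the end. Staff will still see individual cases and allocations, so the change reduces the risk but does not remove it.

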#### Total = 500 mls (500 mcg) in 24 hours

- If no progression in the first cycle, rest for 24 hours, then repeat 50mcg(50mls) every 2 hours for 8 doses
  =400mls(400mcg) in 16 hours.
- If no progression in the second cycle, participants will further undergo Foley's catheterization with the intention to treat as shown in figure 1, while those that are already in labour but needing assistance with contractions may undergo augmentation with oxytocin.

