# **Primary endpoint**

The primary outcome measured would be the proportion of women who have a successful live vaginal delivery without any severe adverse event including: i) failed induction necessitating cesarean section, ii) maternal death, iii) retained placenta, iv) perinatal death, and/or v) neonatal admission to special care nursery.

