# SAMPLE SIZE CALCULATION

If there is a true difference in favour of the experimental treatment of 5%, then 236 patients (118 per treatment arm) will be required to be 90% sure that the upper limit of a one-sided 95% confidence interval (or equivalently a 90% two-sided confidence interval) will exclude a difference in favour of the standard group of more than 5%.

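### The 10% severe-adverse-event criterion at the interim looks shares its term with the primary-endpoint failures and sits at the standard-arm failure rate implied by the sample size, so it poorly separates harm from planned background

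*Protocol*

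**What the plan says.** **Interim analysis.** The first look is set by enrolment: "We will perform an interim analysis after the first 30 participants in each arm have been" enrolled. A second follows at 80 per arm. The Data and Safety Monitoring Committee reviews the results and decides how the study proceeds, using three criteria. The first concerns drug-related adverse events above 25% within 72 hours. The second is "severe adverse events >10% documented within 72 hours post-administration of treatment". The third concerns adverse events above 25% at 4 weeks after discharge. The section does not define a severe adverse event, does not say whether percentages are per arm or pooled, and does not say which dose starts the 72 hours.

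**Primary endpoint.** Success is a live vaginal delivery free of any severe adverse event, with a list introduced as examples: "i) failed induction necessitating cesarean section, ii) maternal death, iii) retained placenta, iv) perinatal death, and/or v) neonatal admission to special care nursery".

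**Sample size calculation.** Assuming a "true difference in favour of the experimental treatment of 5" percentage points, and a margin of 5 points against it, "then 236 patients (118 per treatment arm) will be required to be 90% sure" of showing non-inferiority with a one-sided 95% limit. No event rate is given for either arm.

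**Standard Treatment Arm.** A first cycle of 24 hours; then "If no progression in the first cycle, rest for 24 hours, then repeat 50mcg(50mls) every 2 hours for 8 doses", which takes 16 hours. The Intervention Arm section gives the same timing.

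**Data analysis plan.** Adverse events are counted to discharge and again at 4 weeks.

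**The concern.** The only place where the protocol says what a severe adverse event is lists the components of primary-endpoint failure. If the interim criterion means the same events, its 10% threshold should be compared with the failure rate for which the trial was planned. That rate can be recovered from the sample size. If the two coincide, ordinary caesareans for failed induction and ordinary nursery admissions can take an arm over the line when nothing is wrong, and a crossing tells the committee little.

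Two further gaps affect what the criterion measures. The choice between per-arm and pooled application changes its behaviour markedly. A 72-hour window with no stated start may not cover the full course of treatment.

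**Working it through.** **1. Reproduce 118 per arm.** Inputs from the Sample size calculation: margin 0.05, true difference +0.05, one-sided alpha 0.05 (z = 1.645), power 90% (z = 1.282); allocation 1:1 from Study design. With success rates pS (standard) and pL = pS + 0.05 (low dose):

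n per arm = (1.645 + 1.282)² × [pS(1 − pS) + pL(1 − pL)] / (0.05 + 0.05)²

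At 90% and 95%: 8.564 × (0.0900 + 0.0475) / 0.01 = 117.8, so 118.

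| Success, standard / low dose | n per arm |
|---|---|
| 91% / 96% | 104 |
| **90% / 95%** | **118** |
| 89% / 94% | 133 |
| 85% / 90% | 187 |
| 80% / 85% | 247 |

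The mirror pair, 5% and 10% success, also gives 118 but is implausible for live vaginal delivery. The implied planning failure rates are therefore about 10% on standard and 5% on low dose.

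**2. Turn the criterion into counts.** More than 10% means at least 4 of 30 or 9 of 80 in one arm, and at least 7 of 60 or 17 of 160 pooled. At a true 10%, the expected counts in one arm are 3 and 8, one below each threshold.

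**3. Crossing probabilities, exact binomial.** For one arm with true 72-hour rate p:

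- first look: P(X ≥ 4), X ~ Bin(30, p)
- second look: P(X ≥ 9), X ~ Bin(80, p)
- either look: 1 − Σ b(x; 30, p) b(y; 50, p), summed over x ≤ 3 and x + y ≤ 8, where y counts events in the next 50 women

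| Reading and true 72-hour rate | Look 1 | Look 2 | Either look |
|---|---|---|---|
| One arm, 10% | 0.353 | 0.407 | 0.515 |
| One arm, 8% | 0.216 | 0.189 | 0.300 |
| One arm, 7% | 0.155 | 0.107 | 0.204 |
| One arm, 5% | 0.061 | 0.018 | 0.070 |
| Either arm, 10% / 5% | 0.392 | 0.418 | 0.549 |
| Pooled, 10% / 5% | 0.160 | 0.092 | 0.201 |
| Pooled, 10% / 10% | 0.394 | 0.434 | 0.554 |

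The either-arm figure over both looks is 1 − (1 − 0.515)(1 − 0.070) = 0.549.

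The first row has a second use. A low-dose arm whose failure rate had doubled from the planned 5% to 10% would cross over both looks with probability 0.515, exactly that of a standard arm behaving as planned. The criterion has no reference rate or comparison to tell the two apart.

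**4. The 72-hour window.** Cycle 24 h + rest 24 h + second cycle 16 h = 64 h in either arm, before Foley catheterization. Counted from the first dose, 72 − 64 = 8 hours remain for later steps and their outcomes. Counted from the last dose, the difficulty largely disappears. The protocol does not say which applies.

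**5. Criterion three at an enrolment-triggered look.** The timeline plans 236 women from April 2016 to November 2017: 236 / 20 months is about 12 a month. Assuming about 4 days to discharge (not stated), the 4-week visit falls about 32 days after enrolment, so about 12 of the first 60 would not yet have reached it.

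**The case against.** **A crossing does not stop the trial.** This stands. The committee reviews and decides, and its members include an obstetrician, a paediatrician and a statistician. A reader might infer that the rule is likely to halt a sound trial; the text does not support that. The figures are probabilities of meeting a criterion.

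**The 10% background is inferred.** This stands as a caveat. It is solved from 118 per arm and concerns primary failure, which has no 72-hour limit. The interim section does not cite the primary-endpoint list, the list is not exhaustive, and a caesarean for a reason other than failed induction fails the primary endpoint without being on it. The rate counted under the criterion could therefore be below 10%.

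**Calling a crossing likely needs the least favourable reading.** This also stands. Only per-arm application, both looks combined and no failures lost to the window take the standard arm past one half. Applying the criteria at the second look is itself a natural reading, not an explicit statement. The window point and the crossing figures also pull in opposite directions: if late failures are missed, crossing is less likely, as the 8% and 7% rows show.

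**The window biases the comparison of arms.** A reader might infer that the slower-inducing arm is under-counted. The documents do not show this: both arms have the same 64-hour schedule.

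**Criterion one is already limited to drug-related events.** True, but criterion two carries no such limit.

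**Detail may belong in a committee charter or SAP.** Event coding and table layouts may. But the protocol itself fixes the 10% figure and chooses the term it also uses for primary failure, so that overlap has to be resolved there.

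**Conclusion.** The concern holds in a limited form. As written, criterion two draws on the term that the protocol applies to primary-endpoint failures, and its threshold equals the standard-arm failure rate implied by the sample size. If it is applied per arm and all failures fall within 72 hours, a standard arm performing as planned crosses with probability 35% at 30 women, 41% at 80 and 52% over both looks (55% for either arm). Under other readings that the text allows, the figure over both looks is 20% (pooled at 10% and 5%) or 30% to 20% (one arm at 8% to 7%). The size thus depends on choices that the protocol leaves open. Under any of them, the criterion compares a bare percentage with no stated background and makes no comparison between arms. Late failures could be missed in either arm if the clock starts at the first dose.

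**What to change.** Reconcile the Primary endpoint, Interim analysis and Sample size calculation sections:

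- Either define the events for criterion two separately from primary-endpoint failure, or set its threshold against the planned background rate, stating that rate.
- State that the criterion applies per arm. This should go together with the first change, because per-arm application of the present threshold gives more crossings than pooling at the planning rates.
- Give the committee failed induction and nursery admission by arm, with a confidence interval for the difference.
- List the probability of crossing at the planning rates for each look.
- State when the 72-hour clock starts and reconcile that window with the to-discharge window of the Data analysis plan. A longer window raises the counted rate, so settle it with the threshold.
- Keep the enrolment-triggered looks for acute events. Assess criterion three only among women who have reached the 4-week visit, and review the rest when complete. Holding back each whole look by about five weeks would delay acute safety review and is not needed.

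The cost is wording in the protocol and committee charter and one small extra table. The sample size does not change.
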